3 STUDY PROCEDURES

3.1 Subject Information and Informed Consent

The investigator or his/her representative will explain the nature of the study to the subject and answer all questions regarding this study. Prior to any study-related screening procedures being performed on the subject or any medications being discontinued by the subject in order to participate in this study, the informed consent statement will be reviewed, signed, and dated by the subject or their legally authorized representative (if permitted per local regulations), the person who administered the informed consent, and any other signatories according to local requirements. A copy of the signed informed consent will be given to the subject and the original will be placed in the subject's medical record. An entry must also be made in the subject's dated source documents to confirm that informed consent was obtained before any study-related procedures and that the subject received a signed copy.

Information regarding benefits for subjects and information regarding provisions for treating and/or compensating subjects who are harmed as a consequence of participation in the study can be found in the informed consent form.

Samples for optional biomarker analyses will only be collected if the subject has voluntarily signed and dated a separate written consent form for biomarker testing that has been approved by an Institutional Review Board (IRB)/Independent Ethics Committee (IEC) after the nature of the testing has been explained and the subject has had an opportunity to ask questions. The separate written consent may be part of the main consent form. If the subject does not consent to the biomarker testing, the subject's participation in the study will not be impacted.

Due to the COVID-19 pandemic, it is possible that additional protocol modifications not outlined in this protocol may become necessary. If this situation arises, in addition to the study informed consent, additional verbal consent may be obtained prior to these adaptations or substantial changes in study conduct in accordance with local regulations.

3.2 Medical History

A complete medical history including demographics, history of tobacco, alcohol, and drug use will be taken at screening. The subject's medical history will be updated before the first dose of study drug (Day -1). This updated medical history will serve as the baseline for clinical assessment. A detailed oncology history will also be collected including: histology, date of diagnosis of T-cell prolymphocytic leukemia (T-PLL), any surgical procedures, and treatments administered (including dates and type of modality).

On Day -1, any additional medical history observed after signing of the informed consent but before initial study drug administration and not considered related to study-required procedures will be recorded in the subject's medical history.

3.3 Drug and Alcohol Screen

Subjects should have no history of clinically significant (per investigator's judgment) drug or alcohol abuse within the last 6 months.

3.4 Eastern Cooperative Oncology Group Performance Status

For all subjects, the Eastern Cooperative Oncology Group (ECOG) performance status will be performed as outlined in Section 2.

ECOG performance status will be assessed as follows:

Grade	Description
0	Fully active, able to carry on all predisease performance without restriction.
1	Restricted in physically strenuous activity but ambulatory and able to carry out work of a light or sedentary nature, e.g., light housework, office work.
2	Ambulatory and capable of all self-care but unable to carry out any work activities. Up and about more than 50% of waking hours.
3	Capable of only limited self-care, confined to bed or chair more than 50% of waking hours.
4	Completely disabled. Cannot carry on any self-care. Totally confined to bed or chair.
5	Dead

3.5 Adverse Event Assessment

Please refer to Section 4.

3.6 Concomitant Medication

If a subject reports taking any over-the-counter or prescription medications, vitamins, and/or herbal supplements or if administration of any medication becomes necessary beginning with the screening visit through 30 days after last dose of study drug, the name of the medication, dosage information including dose, route, and frequency, dates of administration including start and end dates, and reason for use must be recorded on the appropriate electronic Case Report Form (eCRF).

Subjects should receive full supportive care during study participation, including transfusion of blood products, fluid and electrolyte replacement, and antibiotics when appropriate. Subjects who use oral contraceptives, hormone-replacement therapy, or other maintenance therapy should continue their use.

General guidelines regarding prohibited and cautionary concomitant medications and dietary restrictions are provided in Protocol Section 5.1, Section 5.3, and Section 5.4. Co-administration of venetoclax and ibrutinib with a strong cytochrome P450 (CYP)3A inhibitor is prohibited during ibrutinib initiation and venetoclax dose ramp-up (refer to the Protocol Section 5.3). Although cautionary, use of a

strong CYP3A inhibitor (after dose ramp-up), moderate CYP3A inhibitors, and strong or moderate CYP3A inducers are allowed if no appropriate therapeutic alternative exists (refer to the Protocol Section 5.4). Dose reductions of venetoclax and ibrutinib are required with concomitant administration of a strong or moderate CYP3A inhibitor (refer to the Protocol Section 5.4). Alternative treatments with less CYP3A induction or inhibition should be considered.

A sample list of prohibited medications and cautionary medications that may interact with study drug is provided in [Appendix B](#). It is not possible to produce a complete list of medications that fall into these categories; if in question, please refer to the appropriate product label.

For guidance regarding medications for management of TLS and neutropenia, refer to the Protocol Section 6.2.

The AbbVie Therapeutic Area Medical Director (TA MD) identified in Section 1 should be contacted if there are any questions regarding concomitant or prior therapy(ies).

3.7 Physical Examination and Ultrasound

A complete physical examination will be performed at screening and a sign- and symptom-directed physical examination for all other scheduled visits as specified in Section 2. The physical examination performed at screening will serve as the baseline physical examination for the entire study. Any significant physical examination findings after the first dose will be recorded as adverse events (AEs). All findings, whether related to an AE or part of each subject's medical history, will be captured on the appropriate eCRF page.

At any time, a symptom-directed physical examination can be performed as deemed necessary by the investigator.

Additionally, spleen and lymph node measurements will be performed during the physical examination or via ultrasound as part of the clinical response assessment at screening and for the scheduled visits as specified in Section 2.

3.8 Height and Weight

Height will be measured at the screening visit only. Body weight will be measured at scheduled visits as specified in Section 2.1. The subject should wear lightweight clothing and no shoes during weighing.

COVID-19 Pandemic-Related Acceptable Protocol Modifications

Due to the COVID-19 pandemic, subject visits may be conducted via phone or video conference. In these situations, height and weight measurements may be performed by the subject or caregiver as needed.

3.9 Vital Signs

Vital sign determinations of systolic and diastolic blood pressure, pulse rate, and body temperature will be obtained at visits as specified in Section 2.1. In addition, vital signs will be measured as clinically

indicated. Blood pressure and pulse rate should be measured after the subject has been sitting for at least 3 minutes.

COVID-19 Pandemic-Related Acceptable Protocol Modifications

Due to the COVID-19 pandemic, subject visits may be conducted via phone or video conference. In these situations, vital signs may be obtained by the subject or caregiver as needed.

3.10 12-Lead Electrocardiogram

A 12-lead electrocardiogram (ECG) will be performed at screening and if clinically indicated. The ECG should be performed prior to blood collection.

The ECGs will be evaluated by an appropriately trained physician at the site ("local reader"). The local reader from the site will sign and date all ECG tracings and will provide his/her global interpretation as a written comment on the tracing using the following categories:

- Normal ECG
- Abnormal ECG – not clinically significant
- Abnormal ECG – clinically significant

Only the local reader's evaluation of the ECG will be collected and documented in the subject's source folder. The automatic machine reading (i.e., machine-generated measurements and interpretation that are automatically printed on the ECG tracing) will not be collected.

COVID-19 Pandemic-Related Acceptable Protocol Modifications

In the event this may not be performed due to study modifications related to the COVID-19 pandemic, perform the 12-lead ECG at the next earliest feasible visit or arrange to have an alternative acceptable local facility perform the ECG for the subject.

3.11 Post-Treatment Follow-Up and Survival Visits

Subjects who discontinue study drug but have not experienced progressive disease (PD) will return for post-treatment follow-up visits. The post-treatment follow-up visits will follow the same schedule as the visit schedule (i.e., Week 4, Week 8, Week 12, Week 16, Week 24, Week 36, and every 12 weeks thereafter). Subjects will return for post-treatment follow-up visits until study completion starting from study drug discontinuation until documented PD or other post-treatment therapies (including stem cell transplantation) are received. Follow-up hematology and disease response assessment data will be collected.

Survival information (i.e., the date and cause of death) will be collected via telephone calls at 6-month intervals or as needed to allow for more frequent survival analyses.

All subjects will be followed for survival information (i.e., date and cause of death, all poststudy anticancer treatment including stem cell transplantation, reasons for poststudy anticancer treatment, regimens, dates of initiation and completion, etc.) unless the subject requests to be withdrawn from the

study survival follow-up; this request must be documented in the subject's medical record and signed by the investigator. If the subject withdraws from study follow-up, the study staff may use a public information source (such as county records) to obtain information about survival status only, as appropriate per local regulations.

3.12 Clinical Laboratory Tests

The blood samples for serum chemistry tests will be collected as specified in Section 2. The baseline laboratory test results for clinical assessment for a particular test will be defined as the last measurement prior to the initial dose of study drug.

A certified laboratory will be utilized to process and provide results for the clinical laboratory tests. Laboratory reference ranges will be obtained prior to the initiation of the study. Required tests are listed in [Table 1](#).

Local laboratories will be utilized to process and provide results for clinical laboratory tests allowing for immediate subject medical management. The principal investigator or subinvestigator will review, initial, and date all laboratory results after receipt from the local laboratory. Local laboratory values will be entered by the site directly onto the appropriate eCRF and laboratory normal ranges and certification for the laboratory that is used will be provided to the AbbVie clinical team if the result is clinically significant (i.e., necessitating an immediate treatment or treatment modification).

For chemistry laboratory tests performed for TLS prophylaxis and monitoring, refer to [Table 1](#).

The baseline laboratory tests will be reviewed for eligibility before study drug administration as specified in Section 2.1.

If a laboratory test value is outside the reference range and the investigator considers the laboratory result to be clinically significant, the investigator will:

- repeat the test to verify the out-of-range value;
- follow the out-of-range value to a satisfactory clinical resolution; or
- discontinue the subject from the study or require the subject to receive treatment.

Table 1. Clinical Laboratory Tests

Hematology	Clinical Chemistry	Other Tests
Hematocrit Hemoglobin Red blood cell count White blood cell count Neutrophils Bands Lymphocytes Monocytes Basophils Eosinophils Platelet count (estimate not acceptable)	Blood urea nitrogen Creatinine Total bilirubin Albumin Alanine aminotransferase Aspartate aminotransferase Alkaline phosphatase Sodium Potassium Calcium Inorganic phosphorus Uric acid ^a Total protein Glucose Bicarbonate	Urine and serum ^b qualitative pregnancy testing human chorionic gonadotropin ^{c,d} Follicle-stimulating hormone ^{b,c,e} Anti-HIV antibody ^b Viral serologies ^{b,f} hepatitis B surface antigen or hepatitis B core antibody HCV antibody (and RNA if HCV antibody is positive) T-cell lymphotropic virus, type 1 ^g SARS-CoV-2 ^b
Coagulation Panel^b		TLS Chemistry Panel
Prothrombin time (PT) AND/OR International normalized ratio (INR) AND/OR Activated partial thromboplastin time (aPTT)	Creatinine clearance (Cockcroft-Gault calculation) Lactate dehydrogenase Serum β2 microglobulin	Creatinine Potassium Calcium Inorganic phosphorus Lactate dehydrogenase Uric acid ^a

CoV = coronavirus; HCV = hepatitis C virus; HIV = human immunodeficiency virus; RNA = ribonucleic acid; SARS = severe acute respiratory syndrome; TLS = tumor lysis syndrome

- a. At room temperature, rasburicase causes enzymatic degradation of the uric acid in blood/plasma/serum samples potentially resulting in spuriously low plasma uric acid assay readings. The following special sample handling procedure must be followed to avoid ex vivo uric acid degradation. Uric acid must be analyzed in plasma. Blood must be collected into prechilled tubes containing heparin anticoagulant. Immediately immerse plasma samples for uric acid measurement in an ice water bath. Plasma samples must be prepared by centrifugation in a precooled centrifuge (4°C). Finally, the plasma must be maintained in an ice water bath and analyzed for uric acid within 4 hours of collection.
- b. Performed at screening and as clinically indicated in Section 2.1.
- c. Females only.
- d. Pregnancy testing is not required for females of nonchildbearing potential.
- e. If needed to determine postmenopausal status.
- f. Monitoring for hepatitis reactivation should be performed per local clinical standards.
- g. Performed at screening in endemic countries only.

Serum Pregnancy Test

A pregnant or breastfeeding female will not be eligible for participation or continuation in this study.

Pregnancy testing should not be performed for postmenopausal women. Determination of postmenopausal status will be made during the screening period based on the subject's history.

A qualitative serum pregnancy test will be performed at screening for all women of childbearing potential.

The serum pregnancy test will be sent to and performed by the local laboratory. If the serum pregnancy test is positive the subject is considered a screen failure. If the serum pregnancy test is borderline, it should be repeated ≥ 3 days later to determine eligibility.

If the repeat serum pregnancy test is:

- positive, the subject is considered a screen failure;
- negative, the subject can be enrolled into the trial;
- still borderline will be considered documentation of continued lack of a positive result, the subject can be enrolled into the study (unless prohibited per local requirements) in the absence of clinical suspicion of pregnancy and other pathological causes of borderline results.

Urine Pregnancy Test

A urine pregnancy test will be performed for all female subjects of childbearing potential on Day –1 and every 4 weeks until 30 days after the last dose of venetoclax or 90 days after the last dose of ibrutinib, whichever the latest, as indicated in Section 2.1. Unless a woman is suspected to have become pregnant, additional pregnancy testing during the clinical trial is not necessary; however, additional urine pregnancy tests can be done at any visit, as needed.

If the urine pregnancy test (which is performed at the site) is negative, begin or continue dosing. If urine pregnancy test is positive, withhold dosing and perform a serum pregnancy test. Pregnant subjects must discontinue from the study.

Viral Serology

Samples will be collected to identify hepatitis B virus (hepatitis B surface antigen or hepatitis B core antibody) and hepatitis C virus (HCV) (HCV antibody and ribonucleic acid [RNA] if HCV antibody is positive) as listed in Table 1.

All subjects enrolled will be followed with clinical laboratory testing at scheduled time points throughout the study. If a subject experiences a sign or symptom that may be suggestive of hepatitis B reactivation and/or a laboratory abnormality suggestive of potential hepatitis B reactivation (e.g., elevated aminotransferases), the investigator should pursue further work-up per clinical practice guidelines/standards. If a subject has positive hepatitis B serology, the subject should be monitored and managed following local medical standard to reduce risk of hepatitis B reactivation.

Viral serology samples are to be collected and sent to the local laboratory for testing.

Human Immunodeficiency Virus

Samples will be collected to identify human immunodeficiency virus (HIV) (anti-HIV antibody) at screening, unless prohibited by local regulations, as listed in Table 1. The investigator must discuss any local reporting requirements to local health agencies with the subject. The site will report confirmed positive results to their health agency per local regulations, if necessary.

Coagulation

Prothrombin time (PT) and activated partial thromboplastin time (aPTT)/international normalized ratio (INR) samples will be collected at screening and on study when clinically indicated.

TLS Risk Assessment and Monitoring

TLS risk assessment will occur at screening as indicated in Section 2.1.

TLS risk assessment will be defined by tumor burden, renal function, and other factors (refer to the Protocol Section 6.2). Tumor burden will be determined by computed tomography (CT) scans and absolute lymphocyte count (ALC) levels.

Laboratory monitoring for TLS will occur during the ramp-up period and once reaching the designated dose during Week 1 as indicated in Section 2.1; TLS monitoring will occur predose (full chemistry panel is required) and at 4, 8, 12, and 24 hours postdose (TLS chemistry panel is required) after each dose escalation of venetoclax (including escalation to 600 mg at Week 8 or thereafter). For the 24-hour sample, a window of –1 hour is allowed. If the predose sample coincides with the 24-hour postdose sample, then the predose sample may be used for both the predose and 24-hour analyses.

Laboratory monitoring for TLS will occur during the ramp-up period and once reaching the designated dose during Week 1 as indicated in Section 2.1; TLS monitoring will occur 4, 8, 12, and 24 hours after each dose escalation. For chemistry laboratory tests performed for TLS monitoring, refer to Table 1.

COVID-19 Pandemic-Related Acceptable Protocol Modifications

If travel restrictions or other changes in local regulations in light of the COVID-19 pandemic prevent the subject from having blood drawn for laboratory testing at the study site, if possible, arrange for subjects to have laboratory work done at a local laboratory, hospital, or other facility. Local laboratory results should be obtained along with reference ranges and kept within the subjects' source documentation. Local laboratory results should be reviewed by the investigator as soon as possible.

If laboratory samples cannot be obtained, study drug administration may be continued provided the investigator has reviewed all prior laboratory results and confirms and discusses with the subject that there is no safety concern for the subject to continue use of the study drug in the absence of current laboratory results. The subject should be scheduled for laboratory draws as soon as feasible within 3 days from the scheduled visit.

3.13 Computed Tomography Scan

A CT scan with contrast (or magnetic resonance imaging [MRI]) will be performed at screening, at Week 24 visit, and at any time during the study as listed in Section 2.1 to confirm a clinical response (complete remission [CR]/complete remission with incomplete blood count recovery [CRi]). A CT scan will be accepted for screening purposes if previously performed within 35 days before the first dose of study drug. Otherwise, a CT scan must be performed within the screening window (28 days) for all subjects.

Contrast-enhanced CT scans including neck, chest, abdomen, and pelvis will be performed for disease assessment using the response evaluation criteria in lymphoma (RECIL)-based T-PLL consensus criteria

assessment schedule¹ (as outlined in [Table 3](#)) as reported by a local radiologist. A contrast-enhanced MRI of the neck, chest, abdomen and pelvis with a noncontrast CT scan of the chest may be used for subjects with whom a contrast CT is medically contraindicated (i.e., subjects with a severe allergy to CT contrast agents or subjects with impaired renal clearance). Whichever method is used at screening, this method should be consistently used throughout the duration of the study.

Any CT scan (or MRI) done throughout the study should be captured on the appropriate eCRF.

3.14 Disease Assessment

All measurable disease must be documented at screening (baseline) before the first dose of study drug for all subjects based on the analysis of clinical laboratory tests (hematology), physical examination, and contrast-enhanced CT scan of involved neck, chest, abdomen, and pelvis (or MRI, if CT scan is medically contraindicated).

For all subjects, clinical response (laboratory and physical examination assessments) will be assessed by the investigator during Weeks 4, 8, 12, 16, 24, 36 and every 12 weeks thereafter, and at the final visit. Note: disease assessments may be performed approximately 7 days before the scheduled visit. The clinical response will be assessed by laboratory tests and physical examination (or ultrasound) using the T-PLL consensus criteria¹ (as outlined in [Table 2](#)).

If clinical response is suggestive of a CR/CRi, a CT scan with contrast (or MRI) should be done for a confirmatory assessment as outlined in [Section 3.13](#).

If a CT scan indicates a CR/CRi, a bone marrow aspirate and biopsy will be required as soon as possible to confirm the clinical response. For subjects who opt-in for correlative biomarker analyses, a portion of the bone marrow aspirate should be split for the optional biomarker collections listed in [Section 3.17](#).

To meet the CR criteria, the CT scan and bone marrow are both required to be negative. Some subjects fulfill all the criteria for a CR but have a persistent anemia, thrombocytopenia, or neutropenia apparently unrelated to T-PLL, but related to drug toxicity. These subjects will be assessed with a response of CRi.

Disease assessment will continue to be performed after the last dose of study drug until disease progression for any subject who has not experienced PD at the time of permanent discontinuation of venetoclax and ibrutinib.

Table 2. Clinical Response Criteria (Based on Physical Examination/Ultrasound and Laboratory Tests)

Group	Parameter	Complete Remission (all met)	Partial Remission (≥ 2 in Group A and ≥ 1 in B met)	Stable Disease (all met)	Progressive Disease (≥ 1 in Group A or B met)
A	Lymph nodes by physical examination/ultrasound	All long-axis diameters to < 1.0 cm	Decrease $\geq 30\%$ in SLD	Change of -29% to $+20\%$ in SLD	Increase in $> 20\%$ in SLD from Nadir ^a
	Spleen by physical examination/ultrasound	Spleen < 13 cm	Decrease $\geq 50\%$ in vertical length beyond normal from baseline	Change of -49% to $+49\%$ beyond normal from baseline	Increase $\geq 50\%$ in vertical length beyond normal from baseline
	Constitutional symptoms	None	Any	Any	Any
	Circulating lymphocyte count	$< 4 \times 10^9/L$	$\leq 30 \times 10^9/L$ and decrease $\geq 50\%$ from baseline	$> 30 \times 10^9/L$ or change of -49% to $+49\%$	Increase $\geq 50\%$ from baseline ^b
	Bone marrow only to assess if CT/MRI confirms CR/CRI	T-PLL cells $< 5\%$ of mononuclear cells	Any	Any	Any
	Any other specific site involvement ^c	None	Any	Any	Any
B	Platelet count	$\geq 100 \times 10^9/L$ (untransfused)	$\geq 100 \times 10^9/L$ or increase $\geq 50\%$ from baseline	Change of -49% to $+49\%$	Decrease of $\geq 50\%$ from baseline
	Hemoglobin	≥ 11.0 g/dL (untransfused, independent of erythropoietin)	≥ 11 g/dL or increase $\geq 50\%$ from baseline	< 11.0 g/dL or increase $< 50\%$ from baseline or decrease < 2 g/dL	Decrease of ≥ 2 g/dL from baseline
	Neutrophils	$\geq 1.5 \times 10^9/L$ (independent of growth factor)	$\geq 1.5 \times 10^9/L$ or increase $\geq 50\%$ from baseline	Change of -49% to $+49\%$	Decrease of $\geq 50\%$ from baseline

CR = complete remission; CRI = complete remission with incomplete blood count recovery; CT = computed tomography; MRI = magnetic resonance imaging; **SLD = sum of long-axis diameters of up to 3 target lesions**; T-PLL = T-cell prolymphocytic leukemia

- Lymphadenopathy: $> 20\%$ increase in the SLD; for small lymph nodes measuring < 1.5 cm after therapy, a minimum increase of 5 mm and a long-axis diameter of ≥ 1.5 cm; or appearance of a new lesion.
- Although no compartment shift is expected under ibrutinib in T-PLL, due to the theoretical possibility of ibrutinib-related redistribution of lymphocytes, increase $\geq 50\%$ from baseline alone may not define progressive disease if it is associated

with lymph node or spleen size decrease or if the isolated increase occurs along the improvement of other disease parameters.

c. Pleural or peritoneal effusion, skin infiltration, central nervous system involvement.

Note: Clinical response assessments are based on physical examination/ultrasound and laboratory test values.

Source: Adapted from the response assessment of the T-PLL consensus criteria.¹

Response definitions for disease assessments are summarized below:¹

Complete Remission (CR): all of the response criteria have to be met.

Complete Remission with Incomplete Marrow Recovery (CRi): all of the CR response criteria in Group A have to be met and at least 1 parameter in Group B is not achieved.

Partial Remission (PR): at least 2 of the parameters in Group A and 1 parameter in Group B need to improve if previously abnormal. If only one parameter of both Groups A and B is abnormal prior to therapy, only 1 parameter needs to improve.

Stable Disease (SD): all of the above criteria have to be met. This state needs to be sustained for at least 3 months.

Progressive Disease (PD): at least one of the above criteria of Group A or Group B has to be met. Constitutional symptoms alone do not define PD.

Table 3. Confirmatory Response Criteria (Based on CT and Bone Marrow Assessments)

Group	Parameter	Complete Remission (all met)	Partial Remission (≥ 2 in Group A and ≥ 1 in B met)	Stable Disease (all met)	Progressive Disease (≥ 1 in Group A or B met)
A	Lymph nodes by CT/MRI	All long-axis diameters to < 1.0 cm	Decrease ≥ 30% in SLD	Change of -29% to +20% in SLD	Increase in > 20% in SLD from Nadir ^a
	Spleen by CT/MRI	Spleen < 13 cm	Decrease ≥ 50% in vertical length beyond normal from baseline	Change of -49% to +49% beyond normal from baseline	Increase ≥ 50% in vertical length beyond normal from baseline
	Constitutional symptoms	None	Any	Any	Any
	Circulating lymphocyte count	< 4 × 10 ⁹ /L	≤ 30 × 10 ⁹ /L and decrease ≥ 50% from baseline	> 30 × 10 ⁹ /L or change of -49% to +49%	Increase ≥ 50% from baseline ^b
	Bone marrow only to assess if CT/MRI confirms CR/CRi	T-PLL cells < 5% of mononuclear cells	Any	Any	Any
	Any other specific site involvement ^c by CT/MRI	None	Any	Any	Any

Group	Parameter	Complete Remission (all met)	Partial Remission (≥ 2 in Group A and ≥ 1 in B met)	Stable Disease (all met)	Progressive Disease (≥ 1 in Group A or B met)
B	Platelet count	≥ 100 × 10 ⁹ /L (untransfused)	≥ 100 × 10 ⁹ /L or increase ≥ 50% from baseline	Change of -49% to +49%	Decrease of ≥ 50% from baseline
	Hemoglobin	≥ 11.0 g/dL (untransfused, independent of erythropoietin)	≥ 11 g/dL or increase ≥ 50% from baseline	< 11.0 g/dL or increase < 50% from baseline or decrease < 2 g/dL	Decrease of ≥ 2 g/dL from baseline
	Neutrophils	≥ 1.5 × 10 ⁹ /L (independent of growth factor)	≥ 1.5 × 10 ⁹ /L or increase ≥ 50% from baseline	Change of -49% to +49%	Decrease of ≥ 50% from baseline

CR = complete remission; CRi = complete remission with incomplete blood count recovery; CT = computed tomography; MRI = magnetic resonance imaging; **SLD = sum of long-axis diameters of up to 3 target lesions**; T-PLL = T-cell prolymphocytic leukemia

- Lymphadenopathy: > 20% increase in the SLD; for small lymph nodes measuring < 1.5 cm after therapy, a minimum increase of 5 mm and a long-axis diameter of ≥ 1.5 cm; or appearance of a new lesion.
- Although no compartment shift is expected under ibrutinib in T-PLL, due to the theoretical possibility of ibrutinib-related redistribution of lymphocytes, increase ≥ 50% from baseline alone may not define progressive disease if it is associated with lymph node or spleen size decrease or if the isolated increase occurs along the improvement of other disease parameters.
- Pleural or peritoneal effusion, skin infiltration, central nervous system involvement.

Note: Confirmatory response assessments based on CT scan and bone marrow aspirate and biopsy.

Source: Adapted from the response assessment of the T-PLL consensus criteria.¹

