3.2 Primary Endpoint

The primary endpoint is the ORR which is defined as the proportion of subjects achieving CR, CRi, or PR as their best overall response (per investigator assessment) in R/R T-PLL subjects based on the T-PLL consensus criteria 2019 (refer to the Operations Manual Section 3.14).^{1,11}

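### The PR column heading in the response tables and the written PR definition can classify the same subject differently, and nothing says which governs the primary endpoint

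*Protocol*

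**What the plan says.** Protocol 3.2 defines the overall response rate (ORR) by a best response of CR, CRi or PR on investigator assessment, and sends the reader to Operations Manual 3.14. Protocol 7.4 requires confirmation for CR and CRi only.

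Operations Manual 3.14 gives the PR rule in two places:

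- **Tables 2 and 3, column heading:** "Partial Remission (≥ 2 in Group A and ≥ 1 in B met". There is no condition on baseline status and no exception. Three of the six Group A cells in this column (constitutional symptoms, bone marrow, other sites) read *Any*. Each Group B cell can be met by a level alone; for hemoglobin it is "≥ 11 g/dL or increase ≥ 50% from baseline".
- **Text between the tables:** "at least 2 of the parameters in Group A and 1 parameter in Group B need to improve if previously abnormal". It continues: "If only one parameter of both Groups A and B is abnormal prior to therapy, only 1 parameter needs to improve".

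The text is introduced with "Response definitions for disease assessments are summarized below". Nothing states whether heading or text prevails. SAP 6.2 names the international study group's criteria and restates neither rule.

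**The concern.** *Met* and *improve if abnormal* are different tests. A count that was normal at entry and stays normal meets a Group B cell without improving. A subject with a single abnormal parameter can satisfy the exception in the text but cannot reach two Group A cells.

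Investigators at about 20 sites in 9 countries make the call, and PR needs no confirmation step. Two sites following different parts of the same section could therefore classify identical subjects differently. The responder count feeds the ORR, the Stage 1 count S and the comparison with the critical value r(S) in Protocol Table 6. In a trial of at most 37 subjects, a single classification can matter.

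**Working it through.** **1. The plan's own design figure.** Inputs from Protocol Table 6: 14 subjects in Stage 1; stop if S ≤ 3; n₂ = 23, 20, 20, 17 and r = 11, 10, 10, 9 for S = 4, 5, 6, ≥ 7. The footnote's example (at least 12 of 37) means efficacy is declared when the total exceeds r(S).

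P(declare efficacy) = Σ over s = 4 to 14 of P(S = s) × P(Bin(n₂(s), p) ≥ r(s) + 1 − s)

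This gives 0.0496 at p = 0.20 and 0.8003 at p = 0.40, which matches the stated 0.05 and 80%. Declaring efficacy at a total equal to r(S) would give 0.0888 and 0.842, so 12 of 37 is the operative threshold. The design calculation is sound; the question is who counts as a responder.

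**2. How to read *Any*.** The progressive disease (PD) column also reads *Any* in the same three rows, under a heading that needs only one cell to be met. If *Any* counted as met, every subject would have PD at every visit. The marrow row is also labelled as assessed only to confirm CR/CRi. *Any* must therefore mean *not counted*, which leaves lymph nodes, spleen and lymphocyte count as the countable Group A parameters for PR.

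**3. Three illustrative subjects** (counts × 10⁹/L, hemoglobin g/dL)

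*Subject 1.* Lymphocytes 120 to 10; nodes, spleen and all Group B values normal throughout.
- Lymphocyte cell: 10 ≤ 30, and the fall is 110/120 = 92%, so it is met.
- The node cell requires a decrease. The spleen cell requires a decrease measured "in vertical length beyond normal from baseline". Neither has a level-only alternative, so normal, unchanged values do not meet them.
- Heading: 1 in Group A, so **not PR**.
- Text: one abnormal parameter, and it improved, so **PR**.
- Under the heading this subject also fails stable disease (a 92% fall to below 30), CR (10 is not < 4) and PD, so no category applies.

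*Subject 2.* Lymphocytes 120 to 10; spleen 20 to 15 cm; nodes normal; hemoglobin 9.0 unchanged; platelets 180 and neutrophils 3.0 throughout. Protocol 5.1 admits such a subject (hemoglobin > 8 g/dL).
- Spleen, taking the table's 13 cm as the limit of normal (an assumption): 20 − 13 = 7 cm beyond normal, a 5 cm decrease, 5/7 = 71%, so met.
- Heading: 2 in Group A, and platelets ≥ 100, so **PR**.
- Text, if an abnormal Group B value must improve: hemoglobin did not, so **not PR**.
- Text, if only abnormal parameters need to improve and a normal one satisfies the rule: **PR**.

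*Subject 3.* Lymphocytes 120 to 10; nodes and spleen normal; platelets 60 to 100; hemoglobin and neutrophils normal.
- Heading: 1 in Group A, so **not PR**.
- Text, exception read as one abnormal parameter in total: two were abnormal, so the exception does not apply and two Group A improvements are needed: **not PR**.
- Text, exception read per group: **PR**.

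**4. All patterns.** Let each of the three countable Group A and three Group B parameters be normal and unchanged, abnormal and improved to threshold, or abnormal and not improved. There are 3⁶ = 729 patterns. Removing the 27 with all of Group A normal leaves 702.

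- PR by heading only: 7 Group A patterns with at least two improved × 6 Group B patterns mixing normal and unimproved with none improved = 42. This takes the stricter reading of the text; under the other reading it is 0.
- PR by text only: 3 if the exception means one abnormal parameter in total. If it applies per group: 3 Group A patterns × 20 Group B patterns = 60.

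These count patterns, not patients. They leave out normal values that deteriorate.

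**5. What one subject can do.** One subject is 1/37 = 2.7 points of ORR at the maximum size and 1/31 = 3.2 points at the smallest two-stage size. One subject can change S from 3 to 4, or the total from 11 to 12 of 37.

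**The case against.** The strongest reply is that there is only one rule. Section 3.14 says response follows the consensus criteria as set out in Table 2. The text summarizes the same source, takes its thresholds from the table, and merely qualifies the heading for parameters that were normal at baseline. On that reading Subject 1 is PR through the exception and Subject 2 is PR because platelets were never abnormal. The two rules also agree for many subjects, such as anyone with two abnormal Group A parameters and one abnormal Group B parameter all reaching threshold.

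Much of this stands. The combined reading is workable, and Subject 2 is a conflict only under one of two plausible readings of the text. But the documents do not state the combined reading. The headings carry no footnote to the exception, and the text is presented as a summary although it contains a condition and an exception that the tables lack. Even a reader who combines the two must still decide whether the exception means one abnormal parameter in total or one per group, which decides Subject 3.

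A reader might also infer that the *Any* cells put every subject at two Group A criteria from the start, so that the table is far more lenient than the text. Step 2 of the working rules that out.

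**Conclusion.** The point holds: the plan as written can classify the same subject both ways on a component of the primary endpoint, and no passage settles which way. Subject 1 shows this directly; Subjects 2 and 3 show that the text itself has more than one reading. The conclusion rests on treating *Any* as not counted.

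The size is one or a few subjects of unknown number, because the documents give no baseline distribution of the parameters. A reader might infer an inflated type I error from lenient PR calls. The documents do not support that: the disagreement can go either way, and any number of percentage points added to the response rate would be invented. What can be said is that one subject is enough to cross the futility boundary or the success threshold. Nor is the sample-size calculation at fault, since it reproduces. And PR is not free of imaging altogether: CT is mandatory at Week 24 and Table 3 has a PR column; only the confirmation requirement is limited to CR/CRi.

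**What to change.** Reconcile the headings of Tables 2 and 3 and the text in Operations Manual 3.14 to one PR rule, checked against the cited 2019 consensus criteria. The rule should state:

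- that *Any* cells do not count toward PR;
- that *improve* means reaching the table threshold, which also settles constitutional symptoms, where no threshold is given;
- whether a Group B value that was normal at baseline satisfies Group B, and whether it must still be at threshold at the assessment;
- whether the exception means one abnormal parameter in total or one per group.

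The third item needs care. If Group B were simply waived when all counts were normal at entry, a subject going from platelets 150 to 90, hemoglobin 12 to 10.5 and neutrophils 2.0 to 1.2 could be PR with no Group B threshold met, which is looser than the heading.

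Refer to the agreed rule in SAP 6.2. Derive PR by program from the recorded component values as a check on the investigator's call, list discordant subjects, and report the ORR both ways.

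The cost is a short wording amendment and some programming; the components are already collected. The ORR could move slightly in either direction.
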